### **8.2.2. Assessment of Severity**

The severity grading of AEs will be assessed as Grade 1, 2, 3, or 4 using the GSI Grading Scale for Severity of Adverse Events and Laboratory Abnormalities ([Appendix 3](#)). For AEs associated with laboratory abnormalities, the event should be graded on the basis of the clinical severity in the context of the underlying conditions; this may or may not be in agreement with the grading of the laboratory abnormality.

### **8.3. Investigator Requirements and Instructions for Reporting Adverse Events and Serious Adverse Events**

Requirements for collection prior to study drug initiation:

After informed consent, but prior to initiation of study medication, the following types of events should be reported on the case report form (CRF/eCRF): all SAEs and adverse events related to protocol-mandated procedures.

All SAEs, regardless of causal relationship, that occur after the subject first consents to participate in the study (i.e., signing the informed consent) and throughout the duration of the study, including the protocol-required 24-week post treatment follow-up period, must be reported to the CRF/eCRF database and Gilead Drug Safety and Public Health (DSPH) as instructed. This also includes any SAEs resulting from protocol-mandated procedures performed from screening onwards.

All AEs, regardless of causal relationship, that occur from initiation of study medication until 4 weeks after last administration of study IMP must be reported to the CRF/eCRF database as instructed.

All AEs should be followed up until resolution or until the adverse event is stable, if possible. Gilead Sciences may request that certain AEs be followed beyond the post-treatment follow up period.

Investigators are not obligated to actively seek SAEs after the 24 week post-treatment follow-up period. However, if the investigator learns of any SAEs that occur after this time and/or if patient is enrolled into the long term follow-up registry, GS-US-334-1113 study, and/or eCRF database has been locked and the event is deemed relevant to the use of IMP, he/she should promptly document and report the event directly to Gilead DSPH within 24 hours of awareness. Gilead DSPH contact information is as follows: Email: [Safety\\[contact]](mailto:[contact]) or [contact]. All AEs and SAEs will be recorded in the CRF/eCRF database within the timelines outlined in the CRF/eCRF completion guideline.

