#### 9.2.1.2. Safety Analysis Set

The primary analysis set for safety analyses will include subjects who were enrolled and have received at least one dose of study drug.

Treatment-emergent data will be analyzed and defined as data collected from the first dose of study drug through the date of last dose of study drug plus 30 days.

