### **9.5.3. Adverse Events**

Clinical and laboratory AEs will be coded using the Medical Dictionary for Regulatory Activities (MedDRA). System Organ Class (SOC), High-Level Group Term (HLGT), High-Level Term (HLT), Preferred Term (PT), and Lower-Level Term (LLT) will be attached to the clinical database.

Events will be summarized on the basis of the date of onset for the event. A treatment-emergent adverse event will be defined as any new or worsening adverse event that begins on or after the date of first dose of study drug up to the date of last dose of study drug plus 30 days.

Summaries (number and percentage of subjects) of treatment-emergent adverse events (by SOC and preferred term) will be provided by cohort:

- All AEs,
- All study drug-related AEs,
- Combined Grade 2, 3 and 4 AEs,
- Combined Grade 3 and 4 AEs,
- Combined Grade 2, 3 and 4 study drug-related AEs,
- Combined Grade 3 and 4 study drug-related AEs,
- All AEs that caused permanent discontinuation from study drug,
- All AEs that caused change in dose or temporary interruption of study drug,
- All SAEs (including death), and
- All study drug-related SAEs

All AEs collected during the course of the study will be presented in data listings.

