**Appendix Table 3. Treatment Phase: Post Treatment Visits Following Primary Study**

	4 Weeks Post Treatment	12 Weeks Post Treatment	24 Weeks Post Treatment
Clinical Assessments			
Vital Signs, Body weight and Height	X	X	X
Symptom-directed Physical Exam	X	X	X
AEs	X	X d	X d
Concomitant Medications	X		
Quality of Life Survey a		X	X
Tanner Pubertal Stage Assessment		X	X
Bone Age Assessment			X
Pregnancy Prevention Counseling c	X	X	
Laboratory Assessments			
Hematology, Chemistry	X	X	
HCV RNA	X	X	X
Viral Sequencing b	X	X	X
Urine Pregnancy Test e	X	X	X

a Quality of life survey will be completed by all subjects at 12-Week and 24-Week Post Treatment visits if a site is approved to use the survey. Subject is to review questionnaire with a parent/guardian and write/mark answers directly onto the questionnaire.

b Plasma samples will be collected and stored for potential HCV sequencing and other virology studies

c Female subjects of childbearing potential should be provided with Urine Pregnancy Test Kits, instructed on their use and requested to continue to self-monitor for pregnancy for 6 months after their last dose of RBV. If required by regulations, additional pregnancy tests beyond 6 months may be added. The subject should be contacted every 4 weeks and asked to report results of the urine pregnancy tests. If a positive urine pregnancy test is reported, the subject should return to the clinic for a serum pregnancy test.

d At Post Treatment Week 12 and 24, only SAEs will be captured

e Including partner pregnancy prevention for male participants (subjects 12 to < 18 years of age and subjects < 12 years of age at the discretion of the Investigator based on subject's pubertal status).

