7.1.5. Treatment-Emergent Adverse Events

7.1.5.1. Definition of Treatment Emergent

Treatment-emergent adverse events (TEAEs) are defined as one or both of the following:

- Any AEs with an onset date on or after the study drug start date and no later than 30 days after permanent discontinuation of study drug.
- Any AEs leading to premature discontinuation of study drug.

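### Non-serious AEs must be reported only to 4 weeks after the last dose but are counted as treatment-emergent to 30 days, so days 29 and 30 are analysed without a duty to collect them (minor)

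*Protocol*

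**What the plan says.** **Collection.** Protocol 8.3 sets the duty for AEs in general: "All AEs, regardless of causal relationship, that occur from initiation of study medication until 4 weeks after last administration of study IMP" go into the CRF/eCRF database. SAEs have a longer duty, from consent through the whole study, "including the protocol-required 24-week post treatment follow-up period".

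The last visit at which non-serious AEs are assessed is the 4-week post-treatment visit, with a window of ±5 days (Protocol 6.5.1). The 12-week and 24-week visits list SAEs only (Protocol 6.5.2 and 6.5.3). Footnote d of Appendix Table 3 confirms this: "At Post Treatment Week 12 and 24, only SAEs will be captured".

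**Analysis.** Protocol 9.2.1.2 defines treatment-emergent data as data collected "from the first dose of study drug through the date of last dose of study drug plus 30 days". Protocol 9.5.3 counts AEs that begin "up to the date of last dose of study drug plus 30 days", and Protocol 9.5 uses the same 30 days. SAP 7.1.5.1 counts an AE with onset "no later than 30 days after permanent discontinuation of study drug". A second bullet there adds, with no date limit, "Any AEs leading to premature discontinuation of study drug".

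SAP 7.1.6 summarises treatment-emergent AEs as the number and percentage of subjects in the Safety Analysis Set, counting each subject once per summary. SAP 7.11 reports no departure from the protocol's safety analyses. That is correct on this point, because the mismatch lies within the protocol and the SAP inherits it.

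**The concern.** The period in which an event must be recorded should cover the period in which it is counted. Here the counting period runs two days longer for non-serious AEs. A child with a first non-serious AE on day 29 or 30 may never have it recorded. The child then stays in the denominator as a subject without that event, because the tables make no adjustment for observed time.

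Safety and tolerability is the primary objective of the Treatment Phase, so the AE tables are central to the report. A reader who sees a 30-day cut-off will take it that non-serious AEs were sought for all 30 days. The plan does not require that, and neither document says so.

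**Working it through.** The plan states no figure for this gap, so there is none to reproduce. The check is window arithmetic followed by an illustration in subjects.

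**Inputs**

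| Quantity | Value | Source |
|---|---|---|
| Reporting limit, all AEs | 4 × 7 = 28 days after last dose | Protocol 8.3 |
| Treatment-emergent limit | 30 days after last dose | Protocol 9.2.1.2, 9.5, 9.5.3; SAP 7.1.5.1 |
| Last visit assessing non-serious AEs | 28 ± 5, i.e. day 23 to day 33 | Protocol 6.5.1 |
| Treatment length | GT-2: 12 × 7 = 84 days; GT-3: 24 × 7 = 168 days | Protocol 3.1.2 |

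**Step 1: the gap by rule.** 30 − 28 = 2 days (days 29 and 30).

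**Step 2: the gap as a share of time**

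- Post-dose window: 2/30 = 6.7%.
- Whole GT-2 window: 84 + 30 = 114 days; 2/114 = 1.8%.
- Whole GT-3 window: 168 + 30 = 198 days; 2/198 = 1.0%.

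**Step 3: does any later contact close it?** No. The Week 12 and Week 24 visits take SAEs only. The four-weekly contacts in Protocol 6.5.1 are for pregnancy test results in females of childbearing potential. A 4-week visit on days 30 to 33 can pick up events from days 29 and 30, although 8.3 does not require them. A visit on days 23 to 28 cannot. Capture therefore depends on the visit date.

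**Step 4: from days to subjects.** A percentage in an AE table changes only if a subject's first event in that category falls on day 29 or 30. The documents give no post-treatment AE rate, so this step rests on an assumption. Let c be the proportion of subjects with a first event in the 30 days after the last dose, at a constant hazard h = −ln(1 − c)/30. The proportion whose first event falls on days 29 and 30 is

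exp(−28h) − exp(−30h) = (1 − c)^(28/30) − (1 − c).

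| Assumed c | Subjects with first event on days 29–30 |
|---|---|
| 5% | 0.3% |
| 10% | 0.6% |
| 20% | 1.2% |
| 30% | 1.7% |
| 50% | 2.4% |

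Within this model each entry is a ceiling for its c, because it supposes that no day 29–30 event is recorded.

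**Step 5: which outputs are touched?**

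- SAEs: collected through 24 weeks after treatment, so not affected.
- Deaths: SAP 7.1.6 summarises all of them, treatment-emergent or not, so not affected.
- Primary safety endpoint (AE leading to permanent discontinuation, Protocol 9.1.2): such an event would normally start by the last dose, and SAP 7.1.5.1 counts it without a date limit. Essentially not affected.
- Laboratory abnormalities: summarised to 30 days, with a 4-week follow-up laboratory window of days 3 to 30 (SAP Table 3-4), so the two agree.
- What remains: the non-serious part of the overall, related and graded AE tables.

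**The case against.** The strongest reply is that the 30-day limit is an inclusion rule and makes no claim of complete observation. Protocol 9.2.1.2 and 9.5 speak of data that were collected, and a 30-day cap over a 4-week visit with a ±5-day window keeps events recorded at a late visit. The study is single-arm and the tables are descriptive, so no between-arm comparison can be biased. This limits the consequence and stands to that extent. It does not remove the mismatch, because the tables give percentages of all treated subjects and nothing tells the reader that the last two days were not systematically covered.

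A reader might infer three stronger things that the documents do not support:

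- **That up to 7 days are lost after a day-23 visit.** 30 − 23 = 7 days do follow such a visit, but days 24 to 28 remain inside the 8.3 reporting duty whatever the visit date. Only days 29 and 30 fall outside it. A visit held early is a question of visit timing, separate from the 28-versus-30 mismatch.
- **That days 29 and 30 go unobserved.** They are not required to be collected. A visit on days 30 to 33 may still record them.
- **That the primary safety result is biased.** The primary safety endpoint and SAEs are covered by rules that do not depend on the 28-day limit.

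**Conclusion.** The mismatch is real and neither document closes it. For non-serious AEs, days 29 and 30 are in the analysis window without a duty to collect them, and capture varies with the date of the 4-week visit. The effect is a small possible undercount of non-serious treatment-emergent AEs in descriptive tables.

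In time, the size is certain: 2 days. In subjects, about 0.3% to 2.4% is an illustration that rests on a constant hazard and an assumed 30-day first-event proportion of 5% to 50%. The upper end needs half of all subjects to have a first event after treatment ends. Severity is minor.

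**What to change.** **If collection is still open.** In Protocol 8.3, replace the 4-week limit for all AEs with 30 days after the last administration of study drug. When the 4-week visit falls before day 30, ask at the next existing contact, for example the Week 12 visit, about non-serious AEs with onset through day 30. Make matching edits to Protocol 6.5.2 and to footnote d of Appendix Table 3, which SAP Appendix 1 repeats. The cost is a short extra question for some subjects and slightly more than one sentence of amendment. Asking at Week 12 relies on recall over several weeks.

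**If collection is complete.** Keep the 30-day cut-off. State in SAP 7.1.5.1 and in the AE tables that non-serious AEs after day 28 were not systematically collected, and give the number of subjects whose last AE assessment fell before day 30. The cost is one table note and one count.

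Shortening the treatment-emergent window to 28 days is the weaker choice. It would drop recorded events from the main tables, depart from Protocol 9.5.3, and separate the AE window from the 30-day laboratory window in Protocol 9.5.4 and SAP 7.2.2.1.

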### Serious Adverse Event Paper Reporting Process

- All SAEs will be recorded on the serious adverse event report form and submitted by emailing or faxing the report form within 24 hours of the investigator's knowledge of the event to the attention of Gilead DSPH or to the designated CRO Pharmacovigilance Representative.

#### **8.4. Gilead Reporting Requirements**

Depending on relevant local legislation or regulations, including the applicable US FDA Code of Federal Regulations, the EU Clinical Trials Directive (2001/20/EC) and relevant updates, and other country-specific legislation or regulations, Gilead may be required to expedite to worldwide regulatory agencies reports of SAEs, serious adverse drug reactions (SADRs), or suspected unexpected serious adverse reactions (SUSARs). In accordance with the EU Clinical Trials Directive (2001/20/EC), Gilead or a specified designee will notify worldwide regulatory agencies and the relevant IEC in concerned Member States of applicable SUSARs as outlined in current regulations.

Assessment of expectedness for SAEs will be determined by Gilead using reference safety information specified in the investigator's brochure or relevant local label as applicable.

All investigators will receive a safety letter notifying them of relevant SUSAR reports. The investigator should notify the IRB or IEC of SUSAR reports as soon as is practical, where this is required by local regulatory agencies, and in accordance with the local institutional policy.

#### **8.5. Special Situations Reports**

##### **8.5.1. Definitions of Special Situations**

Special situation reports include all reports of medication error, abuse, misuse, overdose, reports of adverse events associate with product complaints and pregnancy reports regardless of an associated AE.

Medication error is any unintentional error in the prescribing, dispensing, or administration of a medicinal product while in the control of the health care provider, subject, or consumer.

Abuse is defined as persistent or sporadic intentional excessive use of a medicinal product by a subject.

Misuse is defined as any intentional and inappropriate use of a medicinal product that is not in accordance with the protocol instructions or the local prescribing information.

An overdose is defined as an accidental or intentional administration of a quantity of a medicinal product given per administration or cumulatively which is above the maximum recommended dose as per protocol or in the product labelling (as it applies to the daily dose of the subject in question). In cases of a discrepancy in drug accountability, overdose will be established only when it is clear that the subject has taken the excess dose(s). Overdose cannot be established when the subject cannot account for the discrepancy except in cases in which the investigator has reason to suspect that the subject has taken the additional dose(s).

Product complaint is defined as complaints arising from potential deviations in the manufacture, packaging or distribution of the medicinal product.

## **8.5.2. Instructions for Reporting Special Situations**

### **8.5.2.1. Instructions for Reporting Pregnancies**

The investigator should report all pregnancies that are identified after the subject first consents to participate in the study (i.e., signs the informed consent) and throughout the study, including the post-treatment follow-up period, to the designated CRO Pharmacovigilance Representative using the pregnancy report form within 24 hours of becoming aware of the pregnancy.

The pregnancy itself is not considered an AE nor is an induced elective abortion to terminate a pregnancy without medical reasons.

Any premature termination of pregnancy (e.g., a spontaneous abortion, an induced therapeutic abortion due to complications or other medical reasons) must be reported within 24 hours as an SAE. The underlying medical reason for this procedure should be recorded as the AE term.

A spontaneous abortion is always considered to be an SAE and will be reported as described in Sections 8.1.1 and 8.3. Furthermore, any SAE occurring as an adverse pregnancy outcome post study must be reported directly to Gilead DSPH.

The subject should receive appropriate monitoring and care until the conclusion of the pregnancy. The outcome should be reported to CRO Pharmacovigilance Representative using the pregnancy outcome report form. If the end of the pregnancy occurs after the study has been completed, the outcome should be reported directly to Gilead DSPH. Gilead DSPH contact information is as follows: Email: Safety\[contact] or [contact].

Pregnancies of female partners of male study subjects exposed to Gilead or other study drugs must also be reported and relevant information should be submitted to the CRO Pharmacovigilance Representative using the pregnancy report form and pregnancy outcome report forms within 24 hours. Monitoring of the partner pregnancy should continue until the conclusion of the pregnancy. If the end of the pregnancy occurs after the study has been completed, the outcome should be reported directly to Gilead DSPH, [contact] or email Safety\[contact].

Clinical staff should also report any pregnancies to the Ribavirin Pregnancy Registry at [name] (see also <http://www.ribavirinpregnancyregistry.com>).

Refer to [Appendix 5](#) for Pregnancy Precautions, Definition for Female of Childbearing Potential, and Contraceptive Requirements.

#### 8.5.2.2. Reporting Other Special Situations

All other special situation reports must be reported on the special situations report form and forwarded to the designated CRO Pharmacovigilance Representative within 24 hours of the investigator becoming aware of the situation. These reports must consist of situations that involve study IMP and/or Gilead concomitant medications but do not apply to non-Gilead concomitant medications.

Special situations involving non-Gilead concomitant medications do not need to be reported on the special situations report form; however, for special situations that result in AEs due to a non-Gilead concomitant medication, the AE should be reported on the AE form.

Any inappropriate use of contraindicated medications should not be reported as “misuse,” but may be more appropriately documented as a protocol deviation.

Refer to [Section 8.3](#) and the CRF/eCRF completion guidelines for full instructions on the mechanism of special situations reporting.

All clinical sequelae in relation to these special situation reports will be reported as AEs or SAEs at the same time using the AE eCRF and/or the SAE report form. Details of the symptoms and signs, clinical management and outcome will be reported, when available.

## **9. STATISTICAL CONSIDERATIONS**

### **9.1. Analysis Objectives and Endpoints**

#### **9.1.1. Analysis Objectives**

The primary objective of PK Lead-in Phase of this study is:

- To evaluate the steady state pharmacokinetics (PK) and confirm the dose of SOF in HCV-infected pediatric subjects

The secondary objective of PK Lead-in of this study is:

- To evaluate the safety and tolerability of 7 days of dosing of SOF + RBV in HCV-infected pediatric subjects

The primary objective of Treatment Phase of this study is:

- To evaluate the safety and tolerability of SOF + RBV for 12 or 24 weeks in HCV-infected pediatric subjects with GT-2 or GT-3, respectively

The secondary objectives of Treatment Phase of this study are:

- To determine the antiviral efficacy of SOF + RBV treatment in GT-2 and GT-3 HCV-infected subjects separately, as assessed by the proportion of subjects with SVR 12 weeks after completion of treatment (SVR12)
- To determine the antiviral efficacy of SOF + RBV treatment in GT-2 and GT-3 HCV-infected subjects separately, as assessed by the proportion of subjects with SVR 4 and 24 weeks after completion of treatment (SVR4 and SVR24)
- To evaluate the kinetics of circulating HCV RNA during treatment and after completion of treatment
- To evaluate the emergence of viral resistance to SOF during treatment and after completion of treatment
- To evaluate the palatability of SOF oral granules at Day 1, as applicable.
- To evaluate the effect of growth and development of pediatric subjects during and after treatment.

The exploratory objective of this study is:

- PPD [REDACTED]

### 9.1.2. Primary Endpoints

For the PK Lead-in Phase, the appropriateness of the SOF dose will be assessed by evaluating the steady-state PK of the SOF and its metabolite GS-331007. The primary endpoint is  $AUC_{\tau}$  of GS-331007. Additional steady-state PK parameters of SOF and GS-331007 (e.g.,  $AUC_{last}$ ,  $C_{max}$ ,  $T_{max}$ ,  $C_{last}$ ,  $T_{last}$ ,  $C_{\tau}$ ,  $\lambda_z$ ,  $CL/F$ ,  $V_z/F$  and  $t_{1/2}$  and  $AUC_{\tau}$  of SOF) will be estimated and summarized as described in Section 9.4.

For Treatment Phase, the primary safety endpoint is any AE leading to permanent discontinuation of study drug (s). The key efficacy endpoint is SVR12.

### 9.1.3. Secondary Endpoints

For the PK Lead-in Phase, the secondary endpoints include antiviral activity measurements, including assessment of HCV RNA. AEs leading to permanent discontinuation of study drug(s) will be evaluated as a secondary safety endpoint.

For Treatment Phase, secondary efficacy endpoints include SVR4, SVR24, breakthrough and relapse. Additional efficacy evaluations may include HCV RNA change from Day 1; ALT normalization; viral kinetic parameters, and palatability of SOF oral granules. Secondary safety endpoints of growth and development measurements will be assessed (e.g. height, weight, and Tanner Stage Assessment).

